The Impact of Soft Contact Lens Attributes on Symptoms Associated With Digital Eye Strain in Symptomatic Soft Contact Lens Wearers

NCT03585790

Unique Protocol ID: [name]

TITLE: The impact of soft contact lens surface and optics on symptoms associated with digital eye strain in symptomatic soft contact lens wearers

INVESTIGATORS: [name], OD, PhD; [name] OD

INVESTIGATION SITE: Indiana University

STUDY OVERVIEW

Eye fatigue is a growing concern for the vision community. In large part, this eye fatigue is thought to be exasperated by digital device use, which permeates most all of everyone's lives including work and play. Upwards of three-quarters of the general population may express symptoms of eye fatigue, yet may not know that it is not normal, or that there may be methods to reduce or eliminate eye fatigue. Despite its prevalence, the ocular causes of eye fatigue or unknown and may be related to the cornea/contact lens surface, the accommodative system, the convergence system, overall postural/muscle fatigue, or a combination of these or other causes. The current study aims to systematically investigate the incremental benefits in ameliorating eye fatigue provided by (a) an optimized contact lens spherical prescription, (b) a lens with highly wettable surface, and (c) a lens with optics to aid the accommodative and convergence systems (in addition to a highly wettable lens surface).

PROTOCOL SYNOPSIS

KEY OBJECTIVE	1. Subject-reported eye fatigue (0-100 rating scale)
KEY ENDPOINTS	Superiority (change) of subject-reported rating >8 rating units

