STUDY DESIGN	
The proposed study design is a subject masked, 2 x 2 randomized, crossover (with a baseline reference) comparing the difference in fatigue rating relative to baseline, where the baseline the is the response for subject habitual lenses, with optimized power, worn on their typical (e.g. 2 week, 1 month) replacement schedule. The study design is balanced for residuals with four sources of variation: lens, sequence group, period and participant. To adjust for individual differences prior to study entrance, difference scores will be used as response variables in the analyses. The same number of participants will be randomized to each of two possible lens sequence groups: {A, B}, {B, A}. Baseline will be evaluated prior to any testing of A and B. Specifically, A and B are:
 
Baseline = Subject habitual lenses, with optimized power, habitual replacement A = DAILIES TOTAL 1 sphere (DT1) B = DAILITES TOTAL 1 MULTIFOCAL (DT1 MF)
 
Subjects will be randomized into two equal groups of those that have each of the two sequences ({A, B}, {B, A}) (balanced Latin Square design).

STATISTICAL CONSIDERATIONS	
Sample size	N=42
Hypothesis	
 1. Subject-reported eye fatigue difference scores (lens A – baseline) comparing the change in response for lens A to baseline are <0 (i.e. fatigue rating was improved with lens A over baseline). This hypothesis tests if a lens with enhanced surface (DT1) provides better fatigue ratings than a typical lens without an optimized surface (optimized habitual). 2. Subject-reported eye fatigue difference scores (lens B – baseline) comparing the change in response for lens B to baseline are <0 (i.e. fatigue rating was improved with lens B over baseline). This hypothesis tests if a lens with enhanced surface and enhanced optics (DT1 MF) provides better fatigue ratings than a typical lens without an enhanced surface or enhanced optics (optimized habitual). 3. Subject-reported eye fatigue difference scores (lens B – lens A) comparing the difference in response for lens B to lens A are <0 (i.e. fatigue rating was improved with lens B over lens A). This hypothesis tests if a lens with enhanced surface AND enhanced optics (DT1 MF) provides better fatigue ratings than a lens with only enhanced surface (DT1) characteristics.

Data analysis	SAS PROC MIXED (or R LMER) to fit linear mixed effects model to the normalized ratings data.

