TEST COMPARATOR PRODUCTS	Baseline = Subject habitual lenses, with optimized power, habitual replacement A = DAILIES TOTAL 1 sphere B = DAILITES TOTAL 1 MULTIFOCAL
INCLUSION/EXCLUSION CRITERIA	
 1. Self-reported "eye fatigue" at least once per week attributable to digital device use with baseline. 2. Uses a digital device (phone, tablet, computer, etc) at least 4 hours per day 3. Mobile digital device with active data and text plan, able to receive email and text messages 4. Habitual 2-week or monthly silicone single vision hydrogel soft contact lens use; habitually wearing lenses for 6 or more hours per day for 5 or more days per week for the past 30 days 5. Habitual soft contact lens prescription optimized over-refraction within ± 0.25 D 6. 18-35 years of age 7. No history of issues of eye alignment or binocularity by self-report 8. No doctor diagnosed, self-reported accommodative or binocular vision issues 9. No doctor diagnosed, self-reported ocular surface disease or dry eye requiring regular, ongoing treatment 10. The subject must appear able and willing to adhere to the instructions set forth in this clinical protocol. 11. Vertex corrected refractive cylinder must be -0.75 or less. 12. Visual acuity best correctable to 20/25 or better for each eye 13. The subject must read and sign the Informed Consent form. 14. No active conditions that may prevent soft contact lens wear. 15. Not habitual wearer of any of the test lenses. 16. Photopic pupil size ≥ 4 mm (normal room illumination ~ 100 cd/m²)
OFF LABEL	No.
CLINICAL SUPPLIES REQUESTED FROM ALCON	DAILIES TOTAL 1 sphere DAILITES TOTAL 1 MULTIFOCAL
RESULTS DISSEMINATION	Work will be presented at least one international meeting, such as Global Specialty Lens Symposium or ARVO. The work will also be prepared for submission for peer-reviewed publication (e.g. Optometry and Vision Science). Trade publications may also be prepared at Sponsor's request and expense.
CONFLICT OF INTEREST	None.

PROPOSAL SUMMARY

STUDY DURATION	1 year
----------------	--------

DURATION OF IRB APPROVAL	1 year
GCP TRAINING	Received; 2016-01-12
TYPE OF STUDY	Single center
FUNDING FROM OTHER SOURCES	None.

RATIONALE AND SIGNIFICANCE:

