Furthermore, a recent double-masked, randomized, bilateral cross-over study of pre-presbyopic subjects (Orsborn GSLS 2016) indicates that when two lenses of the same material are compared, one with typical single vision optics and one with optimized optics to decrease accommodative need, individuals report no change in the surface or dryness component of their eye fatigue, but do report a decrease in the optical components of eye fatigue (such as straining). Accordingly, DAILIES TOTAL 1 multifocal, as a single use lens with optimized surface qualities and optimized optics, may be a lens capable of ameliorating eye reported eye fatigue by acting on both the surface and optical sensations that are believed to be the largest components of eye fatigue ([name] 2016).

The current proposal briefly outlines potential strategies to systematically investigate the questions highlighted above. If the results are favorable, the results may serve to help practitioners understand how the DAILIES TOTAL 1 family of products may help ameliorate symptoms of digital eye fatigue.

AIM: To quantify the real-time subject-reported fatigue in symptomatic, non-daily replacement silicone hydrogel soft contact lens wearers and the change in symptomology associated with change to DAILIES TOTAL 1 (sphere), DAILIES TOTAL 1 multifocal (LO Add), relative to normal replacement of habitual lens.

1. No diagnosis of dry eye or ocular surface disease
2. Corneal plane cylinder less than or equal to 0.75 D
3. No diagnosis of any accommodative or convergence problem

METHODS:

STUDY DESIGN: The proposed study design is a subject masked, 2 x 2 randomized, crossover (with a reference) comparing the difference in fatigue rating relative to baseline, where the baseline is the response for subject habitual lenses, with optimized power, worn on their typical (e.g. 2 week, 1 month) replacement schedule. The study design is balanced for residuals with four sources of variation: lens, sequence group, period and participant. To adjust for individual differences prior to study entrance, difference scores will be used as response variables in the analyses. The same number of participants will be randomized to each of two possible lens sequence groups: {A, B}, or {B, A}. Baseline will be evaluated prior to any testing of A and B. Specifically, A and B are:

Baseline = Subject habitual lenses, with optimized power, habitual replacement

A = DAILIES TOTAL 1 sphere

B = DAILITES TOTAL 1 MULTIFOCAL

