Note: To be included in the study, subject-reported eye fatigue at least once per week with baseline (optimized habitual lens, habitual replacement schedule) is required.

Subjects will be randomized into two equal groups of those that have each of the two sequences ({A, B}, {B, A}) (balanced Latin Square design).

At first visit additional baseline, demographic data, and data will be collected. Over refraction will be performed to determine the optimal habitual prescription. Subjects will then be dispensed a new pair of their habitual lenses to be worn on their same replacement cycle. Subjects will, however, not be told that they were given new lenses, but rather to think that these lenses are the same as the ones they brought in. Daily patient-reported outcome measures will be collected for 7 days (± 3 days) of wear.

At the follow-up visit, the subject will be rescreened to assure they still meet the enrollment criteria. If so, in-office measures will be performed. The subject will then be randomized to DT1 sphere or DT1 MF Lo add. Each lens will be worn daily for 7 (± 3) days. After 7 (± 3) days in-office measures will be collected, and the next lens dispensed. There will be 4 visits in all.

Visit 1 = baseline/dispense new optimal habitual on normal replacement schedule

Visit 2 = follow-up habitual/dispense pair 1

Visit 3 = follow-up pair 1/dispense pair 2

Visit 4 = follow-up pair 2/exit

SUBJECTS

Enrollment criteria:

1. Self-reported "eye fatigue" at least once per week WITH OPTIMIZED HABITUAL LENS attributable to digital device use
2. Uses a digital device (phone, tablet, computer, etc) at least 4 hours per day
3. Mobile digital device with active data and text plan, able to receive email and text messages
4. Habitual 2-week or monthly silicone single vision hydrogel soft contact lens use; habitually wearing lenses for 6 or more hours per day for 5 or more days per week for the past 30 days
5. Habitual soft contact lens prescription optimized over-refraction within ± 0.25 D
6. 18-35 years of age
7. No history of issues of eye alignment or binocularity by self-report
8. No doctor diagnosed, self-reported accommodative or binocular vision issues

9. No doctor diagnosed, self-reported ocular surface disease or dry eye requiring regular, ongoing treatment
10. The subject must appear able and willing to adhere to the instructions set forth in this clinical protocol.
11. Vertex corrected refractive cylinder must be -0.75 or less.

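### Hypotheses 1 and 2 are presented as evidence about an enhanced lens surface, but the test lenses also change the replacement schedule, so a surface-specific conclusion does not follow

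*Combined protocol and SAP*

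**What the plan says.** The protocol title names surface and optics as the subject of the study. The Study Overview opens its aims with "The current study aims to systematically investigate the incremental benefits in ameliorating eye fatigue provided by" and then lists an optimised prescription, a highly wettable surface (aim b) and accommodative optics on top of that surface (aim c).

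In the Protocol Synopsis, Hypothesis 1 is that lens A minus baseline is below zero. It adds that this "tests if a lens with enhanced surface (DT1) provides better fatigue ratings than a typical lens without an optimized surface". Hypothesis 2 does the same for lens B, asking whether surface plus optics "provides better fatigue ratings than a typical lens without an enhanced surface or enhanced optics (optimized habitual"). Hypothesis 3 compares lens B with lens A.

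On what the lenses are:

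- **Baseline.** Enrollment criterion 4 requires "Habitual 2-week or monthly silicone single vision hydrogel soft contact lens use". The Aim describes the population as "non-daily replacement silicone hydrogel soft contact lens wearers" and sets the comparison against the habitual lens on its usual replacement schedule.
- **Test lenses.** Both are DAILIES TOTAL 1 products. The Rationale describes the multifocal "as a single use lens with optimized surface qualities and optimized optics".
- **Handling.** Under Study Design, "Subjects will then be dispensed a new pair of their habitual lenses to be worn on their same replacement cycle", and daily ratings are collected for 7 (± 3) days. For the test lenses, "Each lens will be worn daily for 7 (± 3) days".

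**The concern.** The glosses on Hypotheses 1 and 2, aim (b) and the title all invite the reader to take a gain over baseline as an effect of surface, or of surface and optics. Participants also move from a reused lens to a single-use one at the same step. If a fresh lens each day affects fatigue ratings, that effect is included in the same difference score.

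At stake is what a positive result may be said to show. The plan foresees peer-reviewed and possibly trade publication, and guidance to practitioners. A finding that the single-use product is rated better than the habitual regimen would be reported as a finding that the surface relieves eye fatigue.

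**Working it through.** **1. The conditions side by side.**

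| Condition | Surface | Replacement | Optics | Position |
|---|---|---|---|---|
| Baseline | habitual, taken by the plan to be unenhanced | 2-week or monthly | single vision | always first |
| A (DT1 sphere) | DT1 | single use* | single vision | second or third, randomised |
| B (DT1 multifocal) | DT1 | single use | multifocal | second or third, randomised |

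*Single use is stated outright only for the multifocal. For the sphere it is inferred from the shared DAILIES name.

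**2. What each contrast contains**, writing S for surface, R for replacement schedule, O for optics and T for anything tied to baseline coming first (additive effects assumed for simplicity):

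- A − baseline = S + R + T
- B − baseline = S + R + O + T
- B − A = O

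Coded over (baseline, A, B), surface is (0, 1, 1) and replacement schedule is also (0, 1, 1). The columns are identical, so only S + R can be estimated, and only together with T. Separating them would need a condition with the DT1 surface reused, or a single-use lens without it. Neither exists. The planned mixed model has terms for sequence, lens, period, carryover and participant, and none of these separates S from R.

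**3. Whether the new habitual pair removes R.** It makes the baseline lens new at the start. The rating window is 7 − 3 = 4 to 7 + 3 = 10 days, during which the pair is still worn on its own cycle while a single-use lens is replaced each day. Lens ageing is limited, but reuse against single use remains. Because 10 days is short of 14, a pair new at Visit 1 would not reach its scheduled replacement on either a 2-week or a monthly cycle. Splitting results by habitual schedule would therefore barely vary the exposure in question.

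**4. T is not negligible on the plan's own account.** Baseline precedes both test lenses for everyone. Sample Size Determination item 3 reports lower ratings at follow-up in earlier studies. The Lenses section accepts that participants may tell the test lenses from their habitual ones.

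**5. The plan's figure.** Inputs from Sample Size Determination: difference 9 units, SD 18, correlation ρ = 0.50, two-sided α = 0.05, power at least 80%.

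- SD of the difference = 18·√(2(1 − 0.50)) = 18
- Paired t test, non-centrality = √N · 9/18
- Smallest N with power of at least 0.80 = 34, power 0.808. This matches Table 1, as do the other 29 rows.

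This calculation is for B − A, which the point leaves untouched. With 42 completers, power for 9 units is 0.823, 0.886 and 0.943 at ρ = 0.40, 0.50 and 0.60.

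**6. Illustration, under assumption.** Suppose S = 0 and the non-surface terms lower ratings by b units. The documents give no b, so a range is shown. With N = 42, SD 18 and two-sided 0.05, non-centrality = √42 · b / (18·√(2(1 − ρ))). For example, b = 4 and ρ = 0.50 gives 6.481 × 4/18 = 1.44. The chance that A − baseline is significant:

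| b | ρ = 0.40 | ρ = 0.50 | ρ = 0.60 |
|---|---|---|---|
| 0 | 5% | 5% | 5% |
| 2 | 10% | 11% | 12% |
| 4 | 25% | 29% | 35% |
| 6 | 49% | 56% | 66% |
| 8 | 73% | 80% | 88% |

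This applies to a test-lens-minus-baseline difference the SD and correlation that the plan gives for two study lenses.

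**The case against.** The strongest reply is that the hypotheses compare products. Their operative statements are that difference scores are below zero, and the glosses describe lenses without saying in so many words that surface causes the gain. The Aim is already worded as a change to DT1 relative to the habitual lens on its normal schedule. The baseline pair is new and its power optimised. The comparison that sets the sample size is B against A, which is sound on this point.

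All of that stands, and it limits the point to attribution. It does not remove it: the glosses, aim (b) and the title go beyond the Aim, and the plan nowhere notes that replacement schedule changes with surface.

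Three stronger readings are tempting and are not supported:

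- **That lens material also differs.** The documents say the habitual lenses are silicone hydrogel but never state the material of either test lens. Criterion 15 shows only that the products are not the same.
- **That replacement schedule is as likely a cause as surface, or that surface does nothing.** The documents give no figure for either effect. The surface share is unidentified, which is different from small.
- **That calling Hypotheses 1 and 2 regimen comparisons makes them clean.** Fixed order, expected lower follow-up ratings and insecure masking against the habitual lens would still be mixed in.

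**Conclusion.** The point holds as one about attribution. Replacement schedule is fully confounded with surface in A − baseline and B − baseline, so Hypothesis 1 and the surface part of Hypothesis 2 cannot support a surface-specific conclusion, whatever the sample size. This rests on the sphere being single use, as its name implies, and on the habitual pair being reused over the rating window, as its replacement cycle implies.

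The size of any resulting error cannot be derived from the documents. The rates in the illustration show only that non-surface shifts smaller than the 9-unit design difference could often give a significant result. Hypothesis 3, between two DT1 lenses in randomised order, is not affected.

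**What to change.** - Reword Hypotheses 1 and 2, in line with the Aim, as DT1 (or DT1 multifocal) worn as a single-use lens against the participant's habitual lens on its normal replacement schedule.
- Remove the attribution to surface from both hypotheses and from aim (b) of the Study Overview.
- State beside them that these contrasts are not randomised: baseline always comes first, ratings are expected to fall at follow-up, and masking against the habitual lens is not secure.
- Reserve attribute-level inference, on optics, for Hypothesis 3, the randomised and powered comparison.

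The cost is wording and a narrower claim about surface. Sample size, visits, lenses and analysis are unchanged.

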12. Visual acuity best correctable to 20/25 or better for each eye
13. The subject must read and sign the Informed Consent form.
14. No active conditions that may prevent soft contact lens wear.
15. Not habitual wearer of any of the test lenses.
16. Photopic pupil size ≥ 4 mm (normal room illumination ~ 100 cd/m²)

SAMPLE SIZE DETERMINATION

The comparison of interest is DT1 sphere and DT1 MF Lo add, so the sample size calculation was based on detecting a difference between these 2 lenses.

1. The proposed study design is a 2 x 2 crossover design balanced for residuals with four sources of variation: lens, sequence group, period and participant. The same number of participants will be randomized to each of two possible lens sequence groups: {A, B}, {B, A}. Because each lens is preceded by every other lens exactly twice we can check for lens carryover effects; if the carryover effect is the same for each lens type, these effects cancel when comparing differences in lens means.
2. The primary outcome measures are difference in subjective ratings for the current trial lenses normalized to the ratings made at baseline wearing habitual lenses, i.e., ratings will be assessed using an integer scale of 0-100 with semantic anchoring and the rating at baseline will be subtracted from the rating made with each one of the three trial lenses.

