The spherical power of all corrections will be monocularly, distance vision optimized. Specifically, lens powers may not be the same for all types of lenses, due to power-targeting during manufacture, on-eye flexure, etc. Optimization entails providing the lens for each eye that monocularly provides an objective improvement in acuity and up to -0.25 D more for any patient-reported quality improvement. All lenses will be over-labeled, so as to, as best as possible, preserve masking (less blister pack shape). Of note, subjects will not be able to tell the difference between DT1 and DT1 MF (Lo add) because of the same blister shape, but may be able to tell a difference between these and habitual.

OUTCOME MEASURES

Primary:

1. Subject-reported eye fatigue (0-100 rating scale, 0=optimal)

STATISTICAL ANALYSIS

Our primary analysis will use SAS PROC MIXED (or R LMER) to fit linear mixed effects model to the normalized change from baseline ratings data. Because the proposed design is balanced for residuals we could fit the data using PROC GLM if there are no missing data to obtain identical parameter estimates. A separate model will be fit to the data for each rating scale tested. All four sources of variation (lens, sequence group, period and participant) will be included as class variables. We will also test for a carryover effect by including a character-valued variable whose value represents the lens worn in the previous period ('0' assigned to the carryover variable for the first period). Thus, the initial models used to analyze the data include effects for sequence group, lens, period and the overall carryover. Participant-within-sequence group will be included as a random effect. Although LSMEANS due to lens will not be estimable in these models, differences between trial lenses are if we assume the carryover effect is the same for each lens type. Evidence of a significant Lens-by-Period interaction will be handled by running separate analyses within each period using, for example, a *two-sample independent samples t-test*.

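### Criterion 4 does not exclude habitual toric-lens wearers with cylinder up to 0.75 D; for any who enter, H1 and H2 may be attenuated by lost cylinder correction, while H3 is unaffected

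*Combined protocol and SAP*

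**What the plan says.** Item 4 appears in the same words in the synopsis (Inclusion/Exclusion Criteria) and under Subjects, Enrollment criteria. It requires "Habitual 2-week or monthly silicone single vision hydrogel soft contact lens use". Neither place says spherical or non-toric.

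Four other criteria bear on the point:
- Item 5: "Habitual soft contact lens prescription optimized over-refraction within ± 0.25 D".
- Item 11: "Vertex corrected refractive cylinder must be -0.75 or less". The list under Aim has the matching limit, "Corneal plane cylinder less than or equal to 0.75 D".
- Item 12: "Visual acuity best correctable to 20/25 or better for each eye".
- Item 15 excludes habitual wearers of the test lenses, and of no other lens.

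On the lenses, the Study Overview gives the first step in its build-up of benefit as "a) an optimized contact lens spherical prescription", followed by a wettable surface and then by optics. Study Design names "A = DAILIES TOTAL 1 sphere" and gives lens B as the multifocal of the same family, with no mention of cylinder. The Lenses section states: "The spherical power of all corrections will be monocularly, distance vision optimized". Under Study Design, Visit 1 dispenses a new pair of the subject's own habitual lenses, and the ratings from that wear period are the baseline.

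**The concern.** H1 is meant to show what a better surface adds to a typical lens, and H2 what surface and optics add together. Both assume that the refractive correction is otherwise comparable between baseline and test lens.

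For a subject whose habitual lens is toric, it is not. Baseline is rated with cylinder corrected, and A and B are rated with it uncorrected. The difference score then carries a second change, which has nothing to do with surface or add. The rationale section lists blurring among the optical sensations of eyestrain, so the likely direction of this component is a higher fatigue rating on A and B, and hence a smaller apparent improvement over baseline.

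At stake is the interpretation of two of the three listed hypotheses, and of a primary outcome defined as change from the habitual-lens rating.

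**Working it through.** **1. Does any criterion close the gap?**

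| Provision | What it limits | Bars a toric wearer? |
|---|---|---|
| Item 4, single vision | Lens type: excludes multifocals | No |
| Item 5, over-refraction ±0.25 D | Fit of the habitual prescription; sphere or cylinder not specified | No |
| Item 11 and Aim list, cylinder at most 0.75 D | The eye, not the lens worn | No, but it caps what can be lost |
| Item 12, best-correctable acuity | Acuity at best correction, not in the test lens | No |
| Item 15 | Wearers of the test lenses | No |

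A habitual toric wearer with cylinder within the 0.75 D limit is therefore eligible on the text as written, by silence.

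**2. Which contrasts are touched?** Let p be the rise in fatigue rating caused by losing the cylinder correction, and f the share of toric wearers.
- A − baseline and B − baseline: a true benefit of size d appears on average as d − f·p.
- B − A = (B − baseline) − (A − baseline): baseline drops out, and neither test lens is described as correcting cylinder, so p cancels. H3 is not affected.

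**3. The plan's own figure.** Sample Size Determination uses SD 18, correlation 0.50, a 9-unit difference and a two-sided 0.05 paired t test.
- σ_diff = 18·√(2·(1 − 0.50)) = 18.
- Non-centrality δ = √N·d/σ_diff. At N=34, δ = 5.831 × 9/18 = 2.92, and the noncentral t gives power 0.808, as in Table 1. All 30 sample sizes in Table 1 reproduce.
- At the planned 42 completers, δ = 6.481 × 9/18 = 3.24 and power is 0.886.

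**4. Illustration for H1 and H2.** Neither f nor p is in the documents. The ranges below are assumptions, and SD 18 with correlation 0.50 is borrowed from the A-versus-B calculation. Mean = 9 − f·p; variance = 18² + f(1 − f)p², the second term coming from mixing two kinds of subject. N=42.

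| f | p (units) | Mean | SD | Power |
|---|---|---|---|---|
| 0 | any | 9.0 | 18.00 | 0.886 |
| 10% | 3 | 8.7 | 18.02 | 0.863 |
| 10% | 5 | 8.5 | 18.06 | 0.846 |
| 10% | 9 | 8.1 | 18.20 | 0.804 |
| 20% | 3 | 8.4 | 18.04 | 0.838 |
| 20% | 5 | 8.0 | 18.11 | 0.798 |
| 20% | 9 | 7.2 | 18.36 | 0.699 |
| 30% | 3 | 8.1 | 18.05 | 0.810 |
| 30% | 5 | 7.5 | 18.15 | 0.744 |
| 30% | 9 | 6.3 | 18.47 | 0.579 |

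Example: f=20%, p=5 gives mean 9 − 0.2 × 5 = 8.0 and SD √(324 + 0.16 × 25) = √328 = 18.11.

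**5. Would dropping toric wearers from the analysis be better?** With no replacement, f=20% leaves 42 − 8 = 34 subjects and power 0.808 for 9 units. Keeping all 42 gives 0.838 if p=3, 0.798 if p=5 and 0.699 if p=9. A subset estimate can therefore cost more power than it recovers when the penalty is small.

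**The case against.** The strongest reply is that the documents point to spherical correction throughout. The overview speaks of a spherical prescription, the Lenses section optimizes the spherical power of all corrections, and cylinder is capped at 0.75 D. On that reading f is zero and nothing is biased. This stands as evidence of intent. It does not close the gap, because subjects are screened against the criteria, and the word spherical is not in them.

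A reader might go further and infer that toric wearers will be enrolled and that the design hides a real benefit. The documents do not support that:
- They give no toric share and no penalty. The cap limits both who could be wearing a toric and how much correction is lost.
- A 9-unit penalty equals the plan's whole clinically relevant difference, so the last row in each block of the illustration is extreme. Even so, 10% toric wearers with that penalty leaves power at 0.804.
- Sphere is re-optimized for each eye in each lens, which might offset part of the loss.
- The plan claims no power for H1 or H2. Its sample size rests on A versus B.
- The net direction of error in H1 and H2 is not settled. Baseline always comes first, and Sample Size Determination reports that ratings tend to be lower at follow-up, which pushes toward apparent benefit.

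All of these points limit the claim about size. None removes the mixing of effects in any toric wearer who does enter.

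**Conclusion.** The eligibility wording does not exclude habitual toric-lens wearers with cylinder up to 0.75 D, which is at odds with the spherical baseline that the overview assumes. For any such subject, H1 and H2 combine the lens effect with loss of cylinder correction, and that component may attenuate the estimated benefit.

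The amount cannot be derived from the documents. The power figures are illustrative only: they rest on an assumed toric share, an assumed penalty, and an SD and correlation stated for a different comparison. They show a range from negligible (no toric wearers, or 10% with 3 units) to material (20% or more with 5 units or more).

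H3, the contrast that sets the sample size, is unaffected. The conclusion that the plan hides benefit, or that H1 and H2 are underpowered for this reason, does not follow. What remains is a confound that a small change of wording removes.

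**What to change.** In item 4, in both the synopsis and the Subjects section, replace single vision with spherical (non-toric) single vision. Baseline, A and B then all correct sphere only, as the overview intends. The planned N does not change, and no visits or staff are added. The cost is slightly narrower recruitment, since some toric wearers within the 0.75 D limit would be turned away.

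If enrolment has started, record at Visit 1 whether the habitual lens is toric. Keep the all-subject estimates of H1 and H2 as the main result and report the same contrasts in spherical-lens wearers alongside them as a sensitivity analysis. Replacing the main estimate with the subset is not advised, for the reason in step 5 of the working. H3 keeps all subjects.
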